## **7. SAFETY MONITORING**

Safety and tolerability will be evaluated by the investigator from the results of reported signs and symptoms, vital sign measurements, and clinical laboratory test results done as standard of care during the duration of hospitalization. More frequent safety evaluations may be performed if clinically indicated or at the discretion of the investigator.

Randomized, Double-blinded, Placebo-Controlled Clinical Trial to Determine Safety and Feasibility of using an Acellular Sterile Filtered Amniotic Fluid as a Treatment for COVID-19 Patients.

PI: [name]

Version: 17 JUL 2020

Toxicity will be reported using Common Terminology Criteria for Adverse Events (CTCAE) version 5. All AEs will be collected.

## Protocol Deviations

A **protocol deviation** is nonadherence to protocol-specific study procedures or schedules that does not involve inclusion/exclusion criteria, primary objective variable criteria, and/or GCP guidelines. Deviations are considered minor and do not impact the study.

A **protocol violation** is any significant divergence from the protocol, i.e., nonadherence on the part of the patient, the investigator, or the Sponsor to protocol-specific inclusion/exclusion criteria, primary objective variable criteria, and/or GCP guidelines. Protocol violations will be identified and recorded by the study site personnel on the CRF.

Deviations and violations will be reported to the Principal Investigator and the Sponsor and, if necessary (i.e., if the deviation or violation results in an adverse or serious adverse event, the DSMB.

## Adverse Events

An AE may consist of the following:

1. A new event which was not pre-existing at initial study drug administration.
2. A pre-existing event which recurs with increased intensity or increased frequency subsequent to study drug administration.
3. An event which is present at the time of study drug administration which is
4. exacerbated following initial study drug administration.

A Serious Adverse Event (SAE) is defined by FDA and NCI as any adverse drug event (experience) occurring at any dose that in the opinion of either the investigator or sponsor results in any of the following outcomes:

1. Death
2. Life-threatening adverse drug experience
3. Inpatient hospitalization or prolongation of existing hospitalization (for > 24 hours)
4. Persistent or significant incapacity or substantial disruption of the ability to conduct normal life functions
5. Congenital anomaly/birth defect
6. Important Medical Event (IME) that may not result in death, be life threatening, or require hospitalization may be considered a serious adverse drug experience when, based upon medical judgment, it may jeopardize the patient and may require medical or surgical intervention to prevent one of the outcomes listed in this definition

Randomized, Double-blinded, Placebo-Controlled Clinical Trial to Determine Safety and Feasibility of using an Acellular Sterile Filtered Amniotic Fluid as a Treatment for COVID-19 Patients.

PI: [name]

Version: 17 JUL 2020

IRB Notification: Events meeting the University of Utah IRB reporting requirements (<http://www.research.utah.edu/irb/>) will be submitted through the IRBs electronic reporting system within 10 working days.

### **Staggering of patients (first five [5] subjects)**

In order to help identify unforeseeable risks, enrollment will be staggered for the first five patients. Each patient must complete IP administration followed by window of at least 7-days before enrollment of the next subject.

### **Safety Criteria for discontinuation of patient enrollment**

- Occurrence of 1 or more Grade 3 allergic reactions
- Occurrence of 1 or more > Grade 3 organ failure (heart, liver, kidney) per CTCAE definitions.

### **Adverse Event Reporting**

The site investigator is responsible for evaluating all adverse events at their Clinical Center and ensuring that they are properly reported. Adverse events that occur during this study will be recorded. The nature of each experience, date and time (where appropriate) of onset, outcome, course, and relationship to treatment will be documented.

#### Definition of Adverse Event and Serious Adverse Event

Adverse Event (AE) means any untoward medical occurrence associated with the use of an intervention in humans, whether or not considered intervention-related (21 CFR 312.32 (a)). An event constitutes a disease, a set of related signs or symptoms, or a single sign or symptom.

Serious Adverse Event (SAE): A serious adverse event (SAE) for this population is an adverse event that:

- a) results in death; or
- b) is life-threatening (the patient was, in the view of the site investigator, in immediate danger of death from the event as it occurred); or
- c) requires inpatient hospitalization or prolongs an existing hospitalization; or
- d) results in persistent or significant disability or incapacity; or
- e) results in congenital anomaly/birth defect; or
- f) is any other event that, based upon appropriate medical judgment, may jeopardize the patient's health and may require medical or surgical intervention to prevent one of the other outcomes listed in this definition.

Classification of an Adverse Event (Relatedness, Severity, and Expectedness)

Relatedness: The suspected relationship between study interventions and any adverse event will be determined by the site investigator using the criteria below. Relatedness must be assessed by an investigator and may not be assessed by a research coordinator.

- a) Not Related: The event is clearly related to other factors, such as the subject's clinical state, therapeutic interventions, or concomitant drugs administered to the subject.
- b) Possibly Related: The event follows compatible temporal sequence from the time of beginning the assigned study intervention, but could have been produced by other factors such as the subject's clinical state, therapeutic interventions, or concomitant drugs administered to the subject.
- c) Probably Related: The event follows a reasonable temporal sequence from the time of beginning the assigned study intervention, and *cannot be reasonably explained* by other factors such as the subject's clinical state, therapeutic interventions, or concomitant drugs administered to the subject.

Severity: The severity, which is a measure of intensity, of clinical adverse events and laboratory abnormalities will be recorded by the site investigator and categorized. The following guidelines will be used to describe severity.

- Grade 1/Mild: The event is asymptomatic or mild symptoms; clinical or diagnostic observations only; intervention not indicated.
- Grade 2/Moderate: The event is defined as minimal, local or noninvasive intervention indicated; limiting age appropriate instrumental activities of daily living (ADL)
- Grade 3/Severe: The event is medically significant but not immediately life-threatening; hospitalization or prolongation of hospitalization indicated; disabling; limiting self care ADL
- Grade 4/Life-threatening: The event requires urgent intervention.
- Grade 5/Death related to AE.

***Expectedness of the Event: All adverse events, including serious adverse events, will be evaluated as to whether their occurrence was expected or unexpected. An AE will be considered unexpected if the nature, severity, or frequency of the event is not consistent with the risk information described for the study intervention. There are no expected adverse events for IV***

Randomized, Double-blinded, Placebo-Controlled Clinical Trial to Determine Safety and Feasibility of using an Acellular Sterile Filtered Amniotic Fluid as a Treatment for COVID-19 Patients.

PI: [name]

Version: 17 JUL 2020

***administered hAF.***

Treatment or Action Taken: For each adverse event, the site investigator will record whether an intervention was required:

- Medical or surgical procedure
- Concomitant medication: started, changed, or discontinued
- Other, specify
- No action taken

Outcome of Event: Finally, the site investigator will record the clinical outcome of each adverse event as follows:

- Death
- Recovered and the patient returned to baseline status
- Recovered with permanent sequelae
- Symptoms persist

**Time Period for Adverse Events**

For purposes of this study, events that occur following randomization through the Day 180 will be reported as adverse events. Serious adverse events, unexpected medically attended events, and new onset chronic illnesses will be recorded from randomization through Day 180. Specifically, events that occur following informed consent to participate in the study, but prior to actual randomization are not adverse events. These should be recorded as baseline conditions.

**Data Collection Procedures for Adverse Events**

After patient randomization all adverse events (including serious adverse events) will be recorded according to relatedness, severity, and expectedness, as well as their duration and any treatment prescribed. Any medical condition present at the time of randomization, recorded in the patient's baseline history at study entry, which remains unchanged or improves (unless the clinician feels it is clinically relevant), will not be recorded as an adverse event at subsequent evaluations. However, worsening of a medical condition that was present at the time of randomization will be considered a new adverse event and reported.

Adverse events will be coded using the MedDRA coding vocabulary. Coding will be done centrally at the University of Utah Pediatric Department Research Enterprise as this requires specific training.

**Unanticipated Problems (UP)**

Unanticipated problems (UP) are defined as incidents, experiences, or

Randomized, Double-blinded, Placebo-Controlled Clinical Trial to Determine Safety and Feasibility of using an Acellular Sterile Filtered Amniotic Fluid as a Treatment for COVID-19 Patients.

PI: [name]

Version: 17 JUL 2020

outcomes that are unexpected, related or possibly related to participation in the study, and suggest that the research places subjects at a greater risk of harm than was previously known or recognized. The site investigator will report unanticipated problems to the Sponsor (CellReGen) within 24 hours of becoming aware of the event. A detailed completed report will be required to be sent to the (CellReGen) within 3 working days of the event.

In accordance with local IRB requirements, the site investigator may be required to report such unanticipated problems to the IRB. In the event that the medical monitor believes that such an event warrants emergent suspension of enrollment in the trial, they will notify the study investigator and all site investigators to cease enrollment in the trial.

### **Monitoring Serious Adverse Events**

A qualified physician will be designated to fulfill the function of the medical monitor for this study. Site investigators and/or research coordinators will report serious adverse events to the DSMB and CellReGen within 24 hours of becoming aware of the event. A detailed completed report will be required to be sent to the DSMB and CellReGen within 3 working days of the event, and the medical monitor will assess all serious adverse events reported from site investigators.

For each of these serious adverse events, the site investigator will provide sufficient medical history and clinical details for a safety assessment to be made with regard to continuation of the trial. The medical monitor will sign off on each SAE report after review. All SAE reports will be retained at the CellReGen. The SAE reporting process may be incorporated into an Electronic Data Capture (EDC) System in use for the study.

In the unlikely event that the medical monitor believes an unexpected and study-related SAE warrants emergent cessation of enrollment in the trial, CellReGen will immediately be consulted. If these individuals concur with the judgment of the medical monitor CellReGen will notify the study investigator and all site investigators to cease enrollment in the trial. Resumption of enrollment will not occur without consent of the CellReGen

In accordance with local IRB requirements, the site investigator may be required to report such events to the IRB.

### **Follow-up of Serious, Unexpected and Related Adverse Events**

All serious, unexpected and related adverse events, that are unresolved at the time of the patient's termination from the study, will be followed by the site investigators until the events are resolved, patient is lost to follow-up, the adverse event is otherwise explained or has stabilized, or 12 months have

Randomized, Double-blinded, Placebo-Controlled Clinical Trial to Determine Safety and Feasibility of using an Acellular Sterile Filtered Amniotic Fluid as a Treatment for COVID-19 Patients.

PI: [name]

Version: 17 JUL 2020

passed from the time of last study dose.

**PATIENT WITHDRAWAL FROM STUDY:**

A patient may withdraw their consent at any time without effect to their care.

**DISCONTINUATION OF STUDY DRUG:**

hAF-specific treatment will be discontinued if any of the following occur:

- Recurrent Grade 1 or Grade 2 allergic reactions will be determined by the PI
- Grade 3 allergic reactions will be cause to discontinue study drug.
- Patient formally requests to withdraw from the study
- Patient is discharged from the hospital prior to completing the study drug dose regimen
- Patient experiences >Grade 3 organ failure (heart, liver, kidney) per CTCAE definitions.

The study PI, treating clinicians and research staff will monitor closely for the above events, as well as any additional adverse events that occur while the patient is receiving treatment. Adverse events will be reported immediately upon discovery of the event to the PI and assessed for seriousness, relatedness, severity, and expectedness.

Any patient who is randomized, and is subsequently withdrawn due either to patient choice and/or an adverse event (such as allergic reaction) will continue to be monitored per study protocol and per hospital protocol for the duration of their hospitalization. As with patients who complete the protocol, these discontinued patients will still have daily hemodynamic and respiratory support data collected in our database during hospitalization. Any patients who are withdrawn from the study will continue to receive all standard of care monitoring and treatments.

Allergic reactions, regardless of severity, will be assessed and treated by the Principal Investigator based on his or her clinical judgment. This may include use of antihistamines, corticosteroids, or albuterol, depending on the patient's symptoms.

The DSMB will meet regularly to review adverse events, safety analyses and study data and will have access to the actual treatment assignments for each group. The DSMB will meet for a kickoff meeting prior to enrollment of the first patient, and again following 5 patients, 20 patients, 40 patients, and 60 patients. They will also meet as needed if any adverse or serious adverse events occur.

If study drug is discontinued, we will continue to follow the patient and monitor for safety and efficacy endpoints.

### **DISCONTINUATION OF STUDY:**

Events used to trigger modification or stopping of the study pending a safety investigation include:

- Death of any patient
- Any SAE as defined in 21 CFR 312.32
- Three (3) or more of the same Grade 3 or higher AEs (judged by the investigator, medical monitor or sponsor), including infusion site reactions
- One (1) Grade 4 AE
- One (1) anaphylaxis event
- Any event which, in the opinion of the investigator, medical monitor or sponsor, contraindicates further dosing of additional patients
- At the discretion of the Data Safety Monitoring Board (DSMB). The DSMB will meet regularly to review adverse events, safety analyses, and study data. The DSMB will have access to the actual treatment assignments for each group.

Any change to the study stopping rules will be reviewed with the FDA. If the study is suspended, it will not be re-opened without FDA approval.

If the study is discontinued (stopped or suspended) all enrolled patients will be followed for the planned duration of the study.

## **8. STATISTICAL CONSIDERATIONS**

### **Statistical Methods**

This is a trial with patients randomized to two groups: (1) treatment group with hAF administered intravenously (n=30), (2) control group with intravenous administration of a saline control (n=30). Both groups will receive standard of care in addition to these treatments.

Descriptive statistics, including mean (SD) and median (interquartile range), will be used to assess patient characteristics, and clinical and biomarker outcomes. Comparisons will be made stratified on ICU vs floor status at enrollment for variables. Categorical characteristics will be compared using chi-square test or Fisher exact test. Continuous characteristics will be compared using independent samples t-test or Wilcoxon-Mann-Whitney test. 95% Confidence intervals and *p*-values will be reported from all comparisons. Statistical analyses will be conducted in R and STATA, significance will be assessed at the 0.05 level and all tests will be two-tailed.

Safety will be assessed by descriptive reporting of the incidence proportion of study-related safety adverse events in each study group, with one-sided 95%

binomial exact confidence intervals. No statistical hypothesis test is planned to assess safety, which is consistent even with large Phase III trials. The table below displays the number of patients, out of 30, experiencing no adverse event and the corresponding lower-bound of the 95% exact confidence interval.

Number of Patients with no Related Adverse Events	Number of Patients Experiencing a Related Adverse Event	Lower-bound of the 95% Exact Binomial Confidence Interval for Safety
30	0	90%
29	1	85%
28	2	80%
27	3	76%

If there are 30 patients in the hAF group and if all patients in the hAF group complete the study without experiencing an adverse event we will be able to state with 95% confidence that the safety of hAF is at least 90%.

Exploratory outcomes for safety include, but are not limited to, the following:

- Whether the patient experienced any post-randomization AEs while on study (regardless of relatedness to study participation)
- Whether the patient experienced any post-randomization serious AEs while on study
- Whether the patient experienced any post-randomization unexpected AEs while on study.

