Statistical Methodology	
One goal of the analysis is to demonstrate safety, which does not require statistical significance.
 
The other primary goal of the analysis is to assess efficacy of hAF by reducing inflammation in COVID-19 patients, potentially leading to improved clinical outcomes. This will be assessed by measurement of C-reactive protein levels before and after the intervention.
 
Secondary outcomes include:
 

1. Death within 30 days

2. ICU-free days at 30 days

3. Hospital length of stay

4. Need for invasive mechanical ventilation

5. Biomarker levels (interleukin-6, d-dimer, lactate dehydrogenase)

6. Need for ECMO

7. Major adverse cardiac events

8. Patient-reported functional status

\*Enrolled subjects will need to meet blood pressure requirements prior to IP administration, detailed below

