## 2. STUDY OBJECTIVES

The purpose of this study is to explore the effectiveness of processed human amniotic fluid as a treatment for COVID-19. Past use of human amniotic products (i.e., membrane and fluid) has previously been FDA-approved as a human cells, Tissues, and Cellular and Tissue-Based Products (HCT/P) under 21 CFR 1271 for tissue injury; and has been used to reduce inflammation and fibrosis in patients with a variety of ailments. Given this, we hypothesize that intravenously (IV) administered processed sterile filtered amniotic fluid will reduce inflammation in COVID-19 patients, and improve secondary clinical outcomes. Specifically, we hypothesize that patients who receive IV administered hAF will see a 50% reduction in mean C-reactive protein levels following treatment.

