## 6. STUDY DESIGN AND PROCEDURES

1. Patients will be screened via the electronic medical system, and/or noted and communicated to the study team by physicians in the units.
2. Patient will be called for e-consent.
3. Patients of childbearing potential will receive a pregnancy test
4. Enrolled patients will be randomized to intervention or control with random permuted blocks of 2-4 via sealed envelope or secured electronic randomization tool that will be selected after consent. Patients or treating clinicians will not be notified of treatment assignment.
5. Amniotic fluid will be procured by the Cell Therapy and Regenerative Medicine group here at the University of Utah. Product will be delivered, either frozen or thawed, by this group to the relevant hospital unit/floor.
6. After consent, but prior to initial intervention, the following measurements will be collected:
  - a. Demographics (age, sex, height, weight, race/ethnicity, study hospital admit date and time)
  - b. Medical history
  - c. Concomitant medications
  - d. Confirmation of negative pregnancy test, if applicable
  - e. Date of symptom onset
  - f. Date of confirmed SARS-CoV-2 positivity by RT-PCR
  - g. Vital signs (heart rate, blood pressure, oxygen saturation, respiratory rate, temperature)
    - a) Patients must have a blood pressure of <160/96 mmHg prior to receiving study IP
    - b) Patients must have a pulse of <110 beats per minute prior to receiving study IP
  - h. Glasgow Coma Scale
    - a) Patient must have a GCS score of  $\geq 14$  prior to consent
  - i. Respiratory support modality and settings
  - j. Complete blood count with auto differential
  - k. Complete metabolic panel
  - l. Blood glucose (for patients with diabetes)
  - m. Inflammatory biomarkers (interleukin-6, c-reactive protein, d-dimer, lactate dehydrogenase)
  - n. Results of chest x-ray and/or chest CT, if available.
7. Patients will receive either 10ml IV hAF or 10ml normal saline (control) each day for 5 consecutive days. hAF and saline with similar lot numbers will be prepared in order to maintain blinding between both clinicians and patients.
8. For 3 hours following IP administration, patients will be placed on continuous monitoring (e.g., pulse oximetry, blood pressure) and monitored for infusion reactions.
9. Assessments on Days 1-5 will include:
  - a. Intervention or control date and time

- b. Vital signs (heart rate, blood pressure, oxygen saturation, respiratory rate, temperature)

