  - a) Patient must have a blood pressure of <160/96 mmHg prior to receiving study IP
  - b) Patient must have a pulse of <110 beats per minute prior to receiving study IP
    - i. In the event that a patient does not meet blood pressure and/or pulse criteria for IP administration, these vital signs will be rechecked every hour until they have returned to the necessary range.
- c. Glasgow Coma Scale
- d. Respiratory support modality and settings
- e. Blood glucose (for patients with diabetes)
- f. Results of chest x-ray and/or chest CT, if available.
- g. Concomitant medications

10. Day 6 (post-intervention) assessment will include:

- a. Vital signs (heart rate, blood pressure, oxygen saturation, respiratory rate, temperature)
- b. Glasgow Coma Scale
- c. Respiratory support modality and settings
- d. Complete blood count with auto differential\*
- e. Complete metabolic panel\*
- f. Blood glucose (for patients with diabetes)
- g. Inflammatory biomarkers (interleukin-6, c-reactive protein, d-dimer, lactate dehydrogenase)\*
- h. Results of chest x-ray and/or chest CT, if available
- i. Concomitant medications

\*Patients who have been discharged from the hospital prior to Day 6 will be asked to return to the hospital or an outpatient clinic for Day 6 lab work.

11. At ICU discharge (if applicable) and hospital discharge, the following will be gathered:

- a. Intervention or control date and time
- b. Vital signs (heart rate, blood pressure, oxygen saturation, respiratory rate, temperature)
- c. Glasgow Coma Scale
- d. Respiratory support modality and settings
- e. Blood glucose (for patients with diabetes)
- f. Results of chest x-ray and/or chest CT, if available.

12. The following data will be collected following hospital discharge:

- a. Last available results of chest x-ray(s) and/or chest CT(s), if available.
- b. ICU admit and discharge dates and times (if applicable)
- c. Hospital floor admit and discharge dates and times
- d. Dates and times of intubation and extubation (if applicable)
- e. Tracheostomy (if applicable)
- f. ECMO status (and settings, if applicable)
- g. Major adverse cardiac events

- h. Discharge date and time
- i. Discharge location
- j. Concomitant medications
  - a) Including but not limited to current COVID-19 therapies not approved by the FDA, and non-pharmaceutical therapies
- k. Date and time of death (if applicable)

13. Safety assessments will be performed at 30, 60, 90 and 180 days (+/- 7 days) post-discharge

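### Section 8 stratifies comparisons on ICU versus floor but names only unstratified tests, and no single CRP analysis is designated to decide efficacy

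*Combined protocol and SAP*

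**What the plan says.** The Synopsis makes CRP efficacy a primary aim: "The other primary goal of the analysis is to assess efficacy of hAF by reducing inflammation in COVID-19 patients". Section 3 lists CRP before and after treatment as a primary endpoint, and the outcome list in Section 6 repeats it. Section 2 gives the hypothesis that "patients who receive IV administered hAF will see a 50% reduction in mean C-reactive protein levels following treatment".

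The analysis is in Section 8, Statistical Methods. It opens with "Descriptive statistics, including mean (SD) and median (interquartile range), will be used to assess patient characteristics, and clinical and biomarker outcomes". Next comes "Comparisons will be made stratified on ICU vs floor status at enrollment for variables". The tests follow: chi-square or Fisher exact for categorical variables, and for continuous ones, "Continuous characteristics will be compared using independent samples t-test or Wilcoxon-Mann-Whitney test". Confidence intervals and p-values are promised for all comparisons, and "significance will be assessed at the 0.05 level and all tests will be two-tailed".

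The Sample Size Justification gives 30 per group, with no power, CRP standard deviation or planned contrast from which the intended test could be inferred. Section 6 item 4 describes randomization in permuted blocks and mentions no stratification by ICU or floor.

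**The concern.** The stratification sentence and the list of tests do not fit together, and the text allows three readings.

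1. The named tests are run separately among ICU and floor patients.
2. One stratified analysis is intended, but its method is not named.
3. The sentence concerns baseline tables only, because the tests are assigned to characteristics. Biomarker outcomes would then get descriptive statistics alone, and CRP would have no test.

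Under none of these does the plan say which CRP result answers the efficacy question. The choice could therefore be made with the data in hand. Under the first reading, the primary question is split into two underpowered tests with no rule for combining them. A significant floor result beside a non-significant ICU result could be mistaken for a real difference in effect by location.

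**Working it through.** **No figure of the plan to reproduce.** Section 8 contains no CRP power calculation. The consequence has to be worked out under assumptions.

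**Inputs from the documents.** 60 patients, 30 per arm; two-sided 0.05; the 50% figure in Section 2.

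**Assumptions.**
- The between-arm CRP ratio is 0.5. Section 2's 50% is worded as a before/after change in treated patients, so using it between arms is an assumption.
- The effect is the same in ICU and floor patients.
- CRP is analysed on the log scale with SD 0.7, 1.0 or 1.5.
- ICU patients number 3, 6, 10 or 18 of 60, split between arms by chance.
- All 60 Day 6 values are available.

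The pilot results in Section 4 were not among the text reviewed and might narrow these ranges.

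**One test in all 60.** The standardized effect is d = ln 2 / SD and the noncentrality is d × √(30/2). At SD 1.0, d = 0.693 and the noncentrality is 0.693 × 3.873 = 2.68 on 58 df, giving power of 75%. At SD 0.7 it is 96%; at SD 1.5 it is 42%.

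**Separate tests by stratum.** The noncentrality is d / √(1/n₁ + 1/n₂), with power averaged over the hypergeometric distribution of the arm split within the stratum. An empty arm counts as not significant. With floor power F and ICU power I for a given split, the chance that exactly one stratum is significant is F(1 − I) + I(1 − F), averaged in the same way.

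| Log-SD | ICU patients | Floor power | ICU power | Exactly one significant |
|---|---|---|---|---|
| 0.7 | 10 | 93% | 26% | 70% |
| 1.0 | 3 | 73% | 4% | 71% |
| 1.0 | 6 | 70% | 9% | 67% |
| 1.0 | 10 | 67% | 15% | 62% |
| 1.0 | 18 | 59% | 27% | 54% |
| 1.5 | 10 | 36% | 9% | 39% |

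Over the full grid of 3 to 18 ICU patients and SD 0.7 to 1.5, exactly one stratum is significant in 36% to 91% of trials. At SD 1.0 with 10 in ICU, 92% of the split results (0.567 / 0.617) are floor significant and ICU not, although the true effect is identical.

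**False-positive risk.** If success in either stratum were claimed, the error rate would be 1 − 0.95² = 9.75%. The plan states no such rule, so this is a conditional figure.

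**One adjusted analysis (SD 1.0, 10 in ICU).** The ICU/floor term alone, on 57 df, gives 74% against 75% unadjusted when CRP does not differ by location. By simulation of 40,000 trials, it gives 74% against 74% at an ICU–floor gap of 0.5 SD and 74% against 69% at 1 SD. For ANCOVA with baseline log CRP as well, the residual SD is SD × √(1 − ρ²) on 56 df, with information reduced by the factor 56/57 for the extra covariate:

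| Baseline-to-Day-6 correlation ρ | 0 | 0.2 | 0.3 | 0.5 | 0.7 |
|---|---|---|---|---|---|
| Power | 74% | 75% | 78% | 85% | 95% |

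ANCOVA breaks even with the unadjusted test at a correlation of about 0.2. At SD 1.5 its power is 41%, 44%, 51% and 68% for ρ = 0, 0.3, 0.5 and 0.7, against 42% unadjusted.

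**The case against.** The strongest reply is that most of the computed harm belongs to the first reading, which the plan does not state. The third reading is also strained: the passage moves straight from outcomes to comparisons, and a natural reader would apply the t-test or Wilcoxon test to CRP. Section 5 excludes ventilated patients and those on high oxygen support, so the ICU stratum may be very small. With 3 ICU patients and SD 1.0, floor power is 73% against 75% overall, so the floor test loses little. ANCOVA is not dictated by the documents; a van Elteren test or another single stratified analysis would also cure the mismatch. Finally, this is a Phase I/II trial whose safety endpoint is explicitly descriptive.

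Much of this is fair. The power losses are conditional, the ICU share is unknown and ANCOVA is a recommendation. What remains is that under every reading no CRP analysis is designated as decisive. A small ICU group does not help: it leaves the ICU test nearly uninformative (4% power with 3 patients) and makes split results more frequent. The early phase limits the consequences, but the plan calls CRP efficacy a primary goal and sets a significance level for its tests.

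**Conclusion.** The concern holds. The absence of a single deciding CRP analysis is a matter of text and needs no assumption. If the named tests are run by stratum, the primary question gets two results that disagree in roughly 36% to 91% of trials over the range examined, mainly because the smaller stratum is underpowered. That range depends on an assumed halving of CRP between arms, a common effect in both strata, complete Day 6 data, and the stated ranges for SD and ICU share. A false-positive rate of 9.75% would arise only under an either-stratum rule that the plan does not contain. This should be corrected before unblinding; confidence in the size of the effect is medium because the inputs are assumed.

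**What to change.** In Section 8, designate one primary efficacy analysis: a single hAF-versus-placebo comparison of Day 6 CRP with ICU and floor patients together, by ANCOVA on log CRP with baseline log CRP and ICU/floor status at enrolment as covariates, tested once at two-sided 0.05. Report within-stratum CRP estimates with confidence intervals as descriptive, without significance claims. Say whether the stratification sentence covers baseline tables, outcomes or both. Another single stratified test would also resolve the mismatch, provided it is named in advance. The same edit should state the analysis set and the handling of missing Day 6 CRP, since Section 6 relies on discharged patients returning for that sample.

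The cost is a few lines of text, with no change to sample size or visits. Baseline and Day 6 CRP and the ICU and floor admission dates are already collected under Section 6 (items 6, 10 and 12). The covariates use two degrees of freedom, and the model assumes a common effect across strata. The ICU/floor term gains nothing unless CRP differs by location, and baseline adjustment pays only above a correlation of about 0.2; at zero correlation the loss is about one to two percentage points of power at SD 1.0.
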